5.1.3 Visit Windows

Unless otherwise specified, visit-based assessments will be analyzed for each analysis time point according to the nominal visit entered in the Case Report Form (CRF).

5.1.4 Statistical Significance

Unless otherwise specified, hypothesis testing will be performed at the two-sided 0.05 significance level. P-values will be rounded to three decimal places. If a p-value is less than 0.0001 it will be reported as "<0.0001".

5.2 Analysis Populations

The following analysis populations are defined for analysis of subjects:

- 1. **Intent-to-Treat (ITT) Analysis Set**: The ITT analysis set is defined as all Phase II subjects who have signed informed consent. Demographic information and study exit details will be reported separately for those subjects included in the ITT population where no initial implant was attempted.
- 2. **Modified Intent-to-Treat (mITT) Analysis Set**: The mITT analysis set is defined as all Phase II subjects for whom an initial implant is attempted. The mITT analysis set is the primary analysis set for assessment of primary endpoints.
- 3. **Implanted Analysis Set**: The Implanted analysis set is defined as all Phase II subjects who are implanted with the Neuspera SNS system.
- 4. **Responder Analysis Set**: The Responder analysis set is defined as subjects who are implanted with the system and are defined as responders at the Day 28 or Day 42 clinic visit post-implant.
- 5. **Per Protocol (PP) Analysis Set:** The Per Protocol analysis set is defined as implanted subjects who have no protocol deviations that may significantly affect the primary endpoints. The determination of subjects excluded from Per Protocol analysis set will be made prior to analysis.

5.3 Subject Disposition

The number of subjects in each analysis population will be presented along with reason for any exclusions. Subject accountability will be summarized by visit. The number of subjects who are enrolled, attempted but not implanted, implanted, responders on Day 28 and Day 42, and number completing each clinical follow-up visit will be summarized. In addition, the number of subjects who complete the study or exit early will be summarized by reason.

Statistical Analysis Plan Pa			ge 14 of 25
Sponsor	Study		Version
Neuspera	Spera Clinical Study of Neuspera's Implantable Sacral Nerve Stimulation (SNS) System in Patients with Symptoms of Urinary Urgency Incontinence (UUI)		17.0

5.4 Enrollment

During Phase I, subjects will be considered enrolled in the study after signing the informed consent form and after an implant is attempted. The principal investigator will ensure that the subject has met all preoperative eligibility criteria prior to enrollment in the study. The intraoperative eligibility criterion of an appropriate motor response is confirmed during the implant procedure. Subjects in whom an implant is attempted but the appropriate motor response is not observed, will be considered enrolled in the study but will not go on to receive the neurostimulator implant.

During Phase II, subjects will be considered enrolled at the time the subject signs and dates the study specific informed consent form. Subjects who do not meet all eligibility criteria are considered enrolled in the study but will not receive an implant. Subjects in whom an implant is attempted but the appropriate motor response is not observed, will be considered enrolled in the study but will not go on to receive the neurostimulator implant.

5.5 Demographics and Baseline Characteristics

Descriptive statistics will be presented for all clinically relevant baseline demographic, medical history, and clinical characteristic variables.

5.6 Analysis of Study Endpoints

5.6.1 Primary Safety Endpoint

The primary safety endpoint is defined as the incidence of device-related SAEs through the 6-month post-implant follow-up visit. The analysis of the endpoint is the proportion of subjects experiencing a device-related SAE through the 6-month post-implant follow-up.

5.6.1.1 Primary Safety Analysis

There is no planned statistical hypothesis test for the primary safety endpoint. The proportion of subjects experiencing an event, as well as the numerator and denominator, and the associated two-sided exact 95% binomial confidence interval will be provided. Values will be expressed as percentages.

The primary analysis population for the primary safety endpoint is the mITT Analysis set as defined in Section 5.2. Subjects who exit the study prior to reaching the 6-month post-implant follow-up visit without experiencing a device-related SAE will be assumed free of such an event. Any adverse events reported for enrolled subjects who are excluded from mITT Analysis set will be reported separately for the duration of participation in the study.

Statistical Analysis Plan Pa			ge 15 of 25
Sponsor	Study		Version
Neuspera	Clinical Study of Neuspera's Implantable Sacral Nerve Stimulation (SNS) System in Patients with Symptoms of Urinary Urgency Incontinence (UUI)		17.0

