#### **Clinical investigation population**

#### Sample size

The study will be conducted in two operationally seamless phases: Phase I and Phase II. In Phase I, the trial was designed to allow the enrollment of up to 55 subjects and a total of 39 subjects were enrolled. It was anticipated that approximately 40 of the enrolled subjects would have an appropriate motor response during intra-operative testing and would be implanted. A total of 5 subjects failed to achieve an appropriate motor response in Phase I of the trial and were exited from the study. A total of 34 enrolled subjects were implanted with the Neuspera neurostimulator. It was estimated that approximately 33% of the implanted subjects would be determined as non-responders or would drop out of Phase I for other reasons following the sacral nerve stimulation (SNS) trial period. Thus, approximately 27 subjects were to continue in the post-trial period. A total of 34 enrolled subjects were implanted with the Neuspera neurostimulator and all 34 subjects continued into the follow-up phase of the trial.

Protocol no: NSM-004; Version 21.0 Confidential

In Phase II of the trial, the pivotal phase, up to 255 may be enrolled (consented). It is anticipated that approximately 43% of subjects may be screen failures and that the implant success rate will be approximately 95%. Enrollment will be stopped after reaching 120 attempted implants, resulting in approximately 114 successful implants. Revisions will not count towards attempted implants. Subjects who are already enrolled after the last attempted implant will be allowed to be implanted. The primary efficacy endpoint will be assessed in all subjects for whom an initial implant is attempted. Missing data at 6 months will be imputed.

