# 2.6 Medical/Surgical Procedures

The Neuspera SNS neurostimulator implant procedure will be performed in accordance with approved Neuspera Intraoperative Kit Instructions for Use and Neuspera Implantable Sacral Nerve Stimulator Kit Instructions for Use for Model SNS-35 or Model SNS-28. Selection of the model number will be made at the time of the implant.

The subject will be prepped and will undergo local anesthesia, intravenous conscious sedation, or general anesthesia. The S3 foramen will be located per Neuspera's Implantable Sacral Nerve Stimulator Kit Instructions for Use. Following appropriate identification of the sacral nerve location, the neurostimulator will be implanted and stimulation parameters will be confirmed by observing motor responses of anal bellows with or without twitching of the big toe or movement in other toes. If motor responses are not confirmed at S3, the S4 foramen may be located, and motor response confirmed at this location. After confirming the functionality of all electrodes and optimal stimulation parameters, the tethering suture will be clipped, and the incision closed in accordance with approved Neuspera's Implantable Sacral Nerve Stimulator Kit Instructions for Use. A bandage will be placed over the implant site.

If appropriate physiological response cannot be achieved during the implant procedure, the neurostimulator will be removed and the subject will be followed for 30 days post procedure and exited from the study.

In Phase I, subjects determined to be SNS responders after the trial period had lateral and anterior/posterior radiographic images taken to confirm position of the neurostimulator at the final trial visit (day 21, 35 or 49).

Protocol no: NSM-004; Version 21.0 Page 45 of 141 04 Apr 2025
Confidential Neuspera

In Phase II, all subjects will have lateral and anterior/posterior radiographic images taken to confirm position of the neurostimulator at Day 28 clinic visit (if determined a responder) or Day 42 clinic visit (responder or non-responder) post-implant.

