#### 6.1.3.3 Primary Safety Analysis

There is no planned statistical hypothesis test for the primary safety endpoint. The proportion of subjects experiencing an event, as well as the numerator and denominator, and the associated two-sided exact 95% binomial confidence interval will be provided. Values will be expressed as percentages.

The primary analysis population for the primary safety endpoint is the mITT analysis set as defined in Section 6.1.1. Subjects who exit the study prior to reaching the 6-month post-implant follow-up visit without experiencing a device-related SAE will be assumed free of such an event.

Any adverse events reported for enrolled subjects who are excluded from the mITT analysis set will be reported separately for the duration of the study.

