Sample size for Phase II is based on power requirements for the primary efficacy endpoint. A total of 120 attempted implants will provide 85% power for a one-sided 0.025 exact binomial test against the null hypothesis assuming that 1) the implant success rate is 95%, 2) subjects in whom implants are attempted but are not successful are counted as failures, and 3) the overall responder rate, including failed implant attempts, is 63.5%. Calculations are based on a one-sample, one-sided exact test of binomial proportions with a normal approximation and were performed with PASS 2019. To account for

Statistical Analysis Plan Pa			ge 12 of 25
Sponsor	Study		Version
Neuspera	Neuspera Clinical Study of Neuspera's Implantable Sacral Nerve Stimulation (SNS) System in Patients with Symptoms of Urinary Urgency Incontinence (UUI)		17.0

potential attrition prior to implant of up to approximately 43% including screen failures, up to 255 subjects will be enrolled/consented in Phase II. Revisions will not count towards attempted implants. Phase I of the study will be conducted at up to 14 clinical study sites in the US and Europe. Phase II of the study will be conducted in up to 35 clinical sites in the US and Europe. Sample size at any one investigational site will be restricted to no more than 15 subjects enrolled for Phase I and 25 subjects implanted for Phase II. Consideration will be given to lifting the 25 subject implanted cap in Phase II if the investigator makes a request of the sponsor.

5 Statistical Analyses

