5.1.2 Study Day O/Baseline Assessments

Efficacy assessments that are measured over time will use pre-implant data as baseline.

For safety assessments, study day 0 is based on the date of implant (or date of attempted implant for those subjects attempted but not implanted, or date of replacement for subjects undergoing a replacement prior to the assessment of primary endpoint). Time of the event is based on the onset date for the event and calculated from date of implant (or date of attempted implant, or date of replacement, as appropriate). Specific time points for evaluation of safety events (e.g. 6 months) will be defined based on the corresponding visit date for subjects with a visit, or the close of the corresponding visit window for subjects without an event.

Statistical Analysis Plan Pa			ge 13 of 25
Sponsor	Sponsor Study		
Neuspera	Clinical Study of Neuspera's Implantable Sacral Nerve Stimulation (SNS) System in Patients with Symptoms of Urinary Urgency Incontinence (UUI)		17.0

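### Counting early exits as free of device-related SAEs may slightly understate the 6-month risk in implanted subjects, and the safety cut-off is undefined for an event without a Month 6 visit

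*SAP*

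**What the plan says.** The primary safety endpoint is the proportion of subjects with a device-related SAE through the 6-month visit. It is reported with a two-sided exact 95% interval and no hypothesis test (SAP 5.6.1.1, Protocol 6.1.3.3).

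- **Denominator.** SAP 5.2: "The mITT analysis set is defined as all Phase II subjects for whom an initial implant is attempted". Failed attempts are therefore included. Protocol 2.6 says of a failed attempt that the device is removed and "the subject will be followed for 30 days post procedure and exited from the study".
- **Early exits.** SAP 5.6.1.1 says that subjects leaving before the 6-month visit "without experiencing a device-related SAE will be assumed free of such an event". Protocol 6.1.3.3 likewise says that they "will be assumed free of such an event". Failed attempts are not named in either rule, but they exit early and so fall under it.
- **End of the 6-month period.** SAP 5.1.2 uses the visit date for subjects who have the visit, "or the close of the corresponding visit window for subjects without an event".
- **Window close.** Protocol 7.5.9.16 says in its text that a visit window closes when the next visit takes place. Its Table 8 puts Month 6 at 180 days, plus or minus 14.
- **Supporting analyses.** None is planned for this endpoint that uses time to event, exposure or a different assumption about exits. The efficacy endpoint has multiple imputation and a tipping-point analysis (SAP 5.6.4), and the general adverse event tables use a denominator based on follow-up (SAP 5.9).

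**The concern.** For efficacy, treating a dropout as a failure works against the device. For safety, treating a dropout as event-free works in its favour. The exact interval then treats the unobserved part of the six months as if it had been observed. A subject lost at Month 2 with the device in place adds a full unit to the denominator, although four months of device exposure went unseen.

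The cut-off clause is a separate matter. Its second branch refers to subjects lacking an event, where the sense seems to require subjects lacking a visit. As written, a subject who has a device-related SAE and misses the Month 6 visit fits neither branch. Protocol 3.1.2.2.2 reports no serious adverse device effect in Phase II so far, so whether a single event counts could change the headline safety result. The sponsor intends to file for approval on the six-month data (SAP 5.6.3.1).

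**Working it through.** **Inputs.** The SAP (section 4) bases the design on 120 attempts: "A total of 120 attempted implants will provide 85% power for a one-sided 0.025 exact binomial test against the null hypothesis". It assumes that "the implant success rate is 95" per cent. The Protocol synopsis (Sample size) describes stopping at 120 attempts, "resulting in approximately 114 successful implants". The documents give neither the number nor the timing of exits before Month 6. The 5%, 10% and 20% exit fractions and the mid-period timing below are assumptions.

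**Reproducing the plan's split.** 120 × 0.95 = 114 implanted and 6 never implanted, which agrees with the Protocol.

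**Upper limits.** With zero events in n subjects, the exact two-sided 95% upper limit is 1 − 0.025^(1/n). With one or more events it is the Clopper-Pearson limit from the beta distribution. For exits at mid-period, the actuarial effective number is 114 − exits/2:

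- 5%: 6 exits, 114 − 3 = 111
- 10%: 11 exits, 114 − 5.5 = 108.5
- 20%: 23 exits, 114 − 11.5 = 102.5

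| Denominator | 0 events | 1 event | 3 events |
|---|---|---|---|
| 120 attempts (plan) | 3.03% | 4.56% | 7.13% |
| 114 implanted | 3.18% | 4.79% | 7.50% |
| 111 (5% exit) | 3.27% | 4.92% | 7.70% |
| 108.5 (10% exit) | 3.34% | 5.03% | 7.87% |
| 102.5 (20% exit) | 3.53% | 5.32% | 8.32% |

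At zero events the total shift is 0.24 to 0.50 points. Of this, 3.18 − 3.03 = 0.15 points comes only from moving from attempts to implants, which is a change of population and not a bias. The remaining 0.09 to 0.35 points comes from the exits.

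**Harshest case for the point estimate.** Give the six failed attempts the full device risk but only 30 of 180 days of observation, and assume a constant hazard. The crude proportion is then expected to be this share of the true risk:

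- 5% exits: (6 × 30/180 + 114 × 0.975)/120 = 112.15/120 = 93.5%
- 10% exits: (1 + 114 × 0.95)/120 = 109.3/120 = 91.1%
- 20% exits: (1 + 114 × 0.90)/120 = 103.6/120 = 86.3%

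In that case the chance that the upper limit covers a true risk of 5% falls from 98.4% to 97.8%, 97.5% and 96.8%. For a true risk of 10% it falls from 98.4% to 97.3%, 96.7% and 95.3%. For 2% it stays at about 100%. The nominal value for one end of a two-sided 95% interval is 97.5%.

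**Cut-off, case by case.**

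| Month 6 visit | Event | Cut-off in SAP 5.1.2 |
|---|---|---|
| Held | Either | Visit date |
| Missed | No | Window close |
| Missed | Yes | None stated |

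Window close is Day 180 + 14 = 194 by Table 8. By the text of 7.5.9.16 it is the next visit, Month 9, which may be as late as Day 270 + 14 = 284. The two readings differ by up to 90 days. If one real event were lost in this gap, the limit on 120 attempts would move from 4.56% to 3.03% (one event becoming none) or from 5.89% to 4.56% (two becoming one).

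**The case against.** The strongest reply is that much of the apparent missing time carries little device risk. After a failed attempt the device is removed and the subject is followed for 30 days. Implanted subjects who leave are to be explanted and followed for 30 days, and safety data are to be sought from early withdrawals (Protocol 7.4.4). For both groups, event-free is close to true. Risk per attempt is also a legitimate mITT quantity. This stands, and it confines the concern mainly to subjects who leave with the device in place. Such exits do occur: the Protocol synopsis reports two of 34 implanted Phase I subjects who exited without explant, one of them lost to follow-up. That is 5.9% over the whole of Phase I follow-up, with timing not given. The 12 Phase II explants in Protocol 3.1.2.2.2 also have no timing and belong to the group for which the assumption is most defensible.

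A reader might infer that the planned figure is not a 6-month risk at all, or that its upper limit is simply too low. The documents do not support that. The shift is small, and the exact interval is conservative at low risks: even in the harshest case, coverage falls below its nominal 97.5% only for a 5% risk with 20% exits and for a 10% risk. No test or margin depends on the limit.

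A reader might also infer that events in subjects who miss the visit are excluded. SAP 5.1.2 does not say so; it leaves their cut-off unstated, and the clause reads like a slip. It can matter only for events near or after the end of the window. Nor is this interval the only safety inference, since the stopping rules (SAP 8, Protocol 6.4) use exact intervals for fracture, dislodgement and revision. Reporting of numerator, denominator and exits by reason (SAP 5.3, 5.6.1.1) is a further, partial safeguard.

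**Conclusion.** The point holds in a limited form. The plan applies a stated assumption that favours the device, without any supporting analysis, so the crude mITT proportion may understate the 6-month risk in implanted subjects. With zero events the upper limit moves from 3.03% to 3.18% on implanted subjects and to about 3.3% to 3.5% once exits are allowed for. The last range rests on assumed exits of 5% to 20% at mid-period. The true effect depends on how many subjects leave before Month 6 with the device in place, which the documents do not give.

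The cut-off gap and the two definitions of window close are defects in the current text. They are unlikely to matter often, but one affected event would change the limit by more than the exit rule does (4.56% to 3.03%). None of this justifies replacing the mITT proportion as the primary safety figure.

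**What to change.** 1. **SAP 5.6.1.1 and Protocol 6.1.3.3.** Keep the mITT proportion and its exact interval as primary. Beside it, report a 6-month Kaplan-Meier or cumulative-incidence estimate in the Implanted set, which SAP 5.2 already defines, with exits censored and numbers at risk shown. Choose the estimator in advance, state how explants are handled, and name the interval method. The usual Kaplan-Meier standard error is zero when there are no events, so an exact limit on the effective number, as in the working, is one option.
2. **SAP 5.1.2.** Change the second branch of the cut-off so that it applies to subjects without a visit instead of subjects without an event.
3. **Window close.** Define it once for the safety cut-off, and reconcile the text of Protocol 7.5.9.16 with Table 8.
4. **Avoid a complete-case denominator.** Keeping implanted subjects with either an event or full follow-up retains early events but drops early event-free exits, which biases the risk upward.

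The cost is a few sentences and one extra table row, with no new data collection. The downside for the sponsor is a slightly less favourable safety figure beside the primary one.

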5.6.2 Primary Efficacy Endpoint

The primary efficacy endpoint is defined as the percentage of subjects who experience an improvement in UUI symptoms of 50% or more (therapy responders). A therapy responder is defined as experiencing ≥ 50% reduction in the number of UUI episodes at 6 months post-implant, relative to the number of UUI episodes at baseline. For the primary efficacy endpoint, subjects withdrawing for reasons related to a lack of efficacy or due to an adverse event (including death) prior to the 6-month visit will be counted as failures. Those subjects who take OAB medications (after the first two weeks following implant) and prior to the primary efficacy endpoint shall also be considered as device failures.

Calculation of the primary efficacy endpoint will be based on the mITT Analysis Set as defined in Section 5.2.

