For the primary efficacy endpoint, subjects withdrawing for reasons related to a lack of efficacy or due to an adverse event (including death) will be counted as failures. Also, those subjects who take OAB medications (after the first two weeks following implant) and prior to the six-month visit should be adjudicated as device failures. For subjects with missing primary efficacy endpoint results for other reasons (missing diary, subject loss-to-follow-up, etc.), multiple imputation will be used to impute the outcome and results from the imputed data sets combined appropriately to preserve valid inference. Details of the multiple imputation are provided in the Statistical Analysis Plan.

The primary efficacy endpoint will be presented by study visit with descriptive statistics and nominal 95% confidence intervals.

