#### **General exclusion criteria:**

- 1. Has a hemoglobin A1c of >8%, or has diabetes mellitus with glucosuria.
- 2. Has diabetic neuropathy.
- 3. Has interstitial cystitis or bladder pain syndrome as defined by either American Urological Association (AUA) or European Association of Urology (EAU) guidelines, chronic pelvic pain, or recurrent symptomatic urinary tract infections.
- 4. Has skin, orthopedic, neurological, or hematological (bleeding disorder) or anatomical limitations that could prevent successful placement of the neurostimulator.
- 5. Has broken, blistered skin or compromised circulation in the area of the neurostimulator implant.
- 6. Has neurogenic bladder dysfunction such as traumatic or atraumatic myelopathy, multiple sclerosis, Parkinsonism, or history of cerebrovascular accident.
- 7. Has documented urinary retention within 6 months prior to the screening baseline visit date.
- 8. Has clinically significant bladder outlet obstruction.
- 9. Is currently undergoing or has previously undergone pelvic irradiation.
- 10. Is a subject with a mechanical obstruction such as benign prostatic hypertrophy, urethral stricture, or cancer.
- 11. Has current grade 3 or 4 pelvic organ prolapse including cystocele, rectocele, enterocele, procidentia, or vaginal vault prolapse.
- 12. Has symptomatic urinary tract infection (UTI); the subject may be considered for study enrollment if the subject is symptom-free after a full course of treatment prior to beginning the baseline bladder diary. If an asymptomatic bacteriuria is detected during the urinalysis performed at screening, a subject may be enrolled without a waiting period relative to UTI treatment.
- 13. Has primary stress incontinence or mixed incontinence where the stress component predominates or has been treated surgically for stress urinary incontinence within 6 months prior to the screening baseline visit date.
- 14. Has received tibial nerve stimulation (TNS) in the past 3 months for the treatment of overactive bladder or unwilling to stay off TNS therapy for 12-month period following implant.
- 15. Has received treatment of urinary symptoms with any botulinum neurotoxin type-A (BoNT-A) agent in the past 12 months; (e.g. obotulinumtoxinA, Botox®, abobotulinumtoxinA, Dysport®, IncobotulinumtoxinA, Xeomin®).

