#### 7.5.8.2 Phase II

The implant procedure and post procedure care in Phase II is consistent with that performed in Phase I. In the first 28 days post implant, subjects will receive 2 hours of continuous daily stimulation using the external Wireless Transmitter. At the end of 28 days treatment efficacy will be assessed. Subjects with acceptable efficacy (≥50% reduction in number of UUI episodes) will be considered a responder and will continue in the post-implant follow-up with 2 hours of daily stimulation using the Wireless Transmitter. Those with less than acceptable efficacy (<50% reduction in number of UUI episodes) will continue for an additional 14-day period with 4 hours of daily stimulation with the Wireless Transmitter. After 14 days of 4 hours of daily stimulation those subjects with ≥50% reduction in number of UUI episodes will be considered a responder. Those subjects who increased to 4 hours of daily stimulation, regardless of responder or non-responder status at the end of the 42-day period will continue in the post-implant follow-up with 4 hours of daily stimulation. A decision to continue a subject with less than a 50% improvement at the end of the 42-day period will be made by the investigator based on what they determine is in the best interest of the subject.

The following will be completed and documented using the appropriate CRFs during the post-implant follow-up visits:

- Review of subject therapy and usage history
- Device data will be periodically recorded
- Adjustments of device stimulation parameters on Clinician Programmer
- Vital Signs
- Changes to medication (including OAB medications) and OAB therapies

Protocol no: NSM-004; Version 21.0 Page 85 of 141 04 Apr 2025
Confidential Neuspera

- Adverse event assessment
- Wound check
- 72- hour bladder diary (reviewed)
- Stimulation Diary (reviewed)
- Wexner Scale (reviewed, only in subjects with FI at baseline)

During the post-implant period, subjects will complete a 72-hour bladder diary documenting the number of voids, voided volume (specified times), leaks, urgency episodes (leaks and voids), and pad use prior to each clinic visit.

During the Therapy Session, when the subject is wearing the Wireless Transmitter and receiving stimulation therapy, the overall goal is to feel a comfortable level of stimulation. Subjects must complete a Stimulation Dairy to document daily therapy use.

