# 7.5.9.7 Conservative OAB Therapy Log

All current OAB therapies subjects are using will be documented at the screening baseline visit. Any changes to OAB therapies will be recorded at each subsequent study visit until study exit (Phase I) and 12-months post-implant (Phase II).

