5.6.4 Handling of Missing Data

All attempts will be made to limit the amount of missing data. No attempt will be made to impute missing data for any analyses except for the primary and secondary efficacy endpoints as specified below in the mITT analysis set. If a data point is missing, that data point will not contribute to that portion of the analysis. The number of evaluable observations will be reported in the analysis so that extent of missing data can be assessed.

For the following efficacy endpoints, subjects withdrawing for reasons related to a lack of efficacy or due to an adverse event (including death) will be counted as failures if they do not have evaluable data for the endpoint:

- The percentage of all implanted subjects who experience an improvement in UUI symptoms of 50% or more at 6-month post-implant (primary efficacy endpoint)
- The percentage of all implanted subjects who experience an improvement in UUI symptoms of 50% or more at 12-month post-implant (secondary efficacy endpoint)

For the continuous efficacy endpoints that may be used for labeling claims, no change from baseline values will be assumed for subjects withdrawing for reasons related to a lack of efficacy or due to an adverse event (including death) if they do not have evaluable data for the endpoint.

If data on these endpoints are missing for other reasons (missing diary or ICIQ-OAB questionnaire, subject loss-to-follow-up, etc.), multiple imputation will be used to impute the outcome. Results from the imputed data sets will be combined appropriately to preserve valid inference. A tipping point analysis will also be performed, examining outcomes for the primary efficacy endpoint for all possible permutations of imputed values for missing subjects.

Multiple imputation will be based on the following variables and will use full conditional specification and 100 imputed data sets. Variables to be included in the imputation model include:

- baseline age, investigational site, baseline UUI episodes, and all available follow-up visit UUI
 episodes through 6 months or 12 months (for the primary and secondary efficacy endpoints of
 improvement in UUI)
- baseline age, investigational site, baseline score, and all available follow-up visit scores through 6 months or 12 months (for the remaining secondary efficacy endpoints that may be used for labeling claims)

S	tatistical Analysis Plan	Pa	ge 21 of 25
Sponsor	Study		Version

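### The failure rule for added OAB treatment names only OAB medications, so tibial nerve stimulation (and possibly BoNT-A) before Month 6 can be credited to the device, and the labeling secondaries have no matching sensitivity analysis

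*SAP*

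**What the plan says.** **Primary endpoint.** SAP 5.6.2 states: "Those subjects who take OAB medications (after the first two weeks following implant") and before the primary endpoint count as device failures. Protocol 6.1.2.3 has the same rule: "those subjects who take OAB medications (after the first two weeks following implant) and prior to the six-month visit should be adjudicated as device failures". Neither document defines OAB medications.

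**Other OAB treatments.** The protocol treats these as a separate category.
- Protocol 1.1.2 places the oral drugs in the second line. Protocol 1.1.3 places percutaneous tibial nerve stimulation and BoNT-A in the third.
- Protocol 7.5.3 requires both medications and therapies to be stopped before the baseline diary, but its requirement to stay off afterwards names medications only.
- Exclusion 14 bars anyone "unwilling to stay off TNS therapy for 12-month period following implant". Exclusion 15 on BoNT-A looks back 12 months and sets nothing for the period after implant.
- Follow-up visits record "Changes to medication (including OAB medications) and OAB therapies" (Protocol 7.5.8.2). Protocol 7.5.9.7 adds: "Any changes to OAB therapies will be recorded at each subsequent study visit until study exit (Phase I) and 12-months post-implant (Phase II").

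**Labeling secondaries.** For the continuous endpoints, SAP 5.6.4 says that "no change from baseline values will be assumed for subjects withdrawing for reasons related to a lack of efficacy" or an adverse event, and only where evaluable data are lacking. Data missing for other reasons are multiply imputed. Nothing is said about added OAB drugs or therapies. The ICIQ-OABqol 10-point responder endpoint is not among the endpoints given a failure rule.

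**Planned sensitivity analysis.** SAP 5.6.2.2 has one for OAB medication. It covers the primary endpoint only and uses the subjects' actual outcomes.

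**The concern.** There is no control arm, so any improvement between baseline and Month 6 is attributed to the device. Baseline is measured off both drugs and other OAB therapies. Month 6 is protected in the analysis against drugs only. Therapy changes are collected, but no analysis rule uses them.

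Two consequences follow. First, a subject who receives TNS in, say, month 4 and then halves the UUI count is a responder, while a subject who does the same on an oral drug is a failure. Second, the drug user's Month 6 diary is set aside in the primary test but enters the next test in the hierarchy, change in UUI episodes, at its on-drug value. The reader of the label has no analysis showing how much that matters.

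**Working it through.** **1. How the plan as written handles each case (use after week two, before Month 6, with a completed Month 6 diary)**

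| Added treatment | Primary endpoint | Labeling secondaries |
|---|---|---|
| OAB medication | Failure | Observed on-drug value |
| TNS | Responder if the diary improves by at least 50% | Observed value |
| BoNT-A | Failure only if read as an OAB medication | Observed value |
| Conservative or behavioural measure | Responder if the diary improves by at least 50% | Observed value |

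**2. The plan's own figures.** Inputs from SAP 4 and 5.6.2.1: n = 120, null 0.50, one-sided alpha 0.025, assumed rate 0.635, minimum success 72/120.
- Exact tails under p = 0.50: P(X ≥ 72) = 0.0177 and P(X ≥ 71) = 0.0274. The 72/120 threshold is reproduced.
- Power by normal approximation: (0.135 × √120 − 1.96 × 0.5) / √(0.635 × 0.365) = (1.479 − 0.980) / 0.481 = 1.04, which gives 85.0%. The stated 85% is reproduced. The exact power at 72/120 is 81.4%.

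The fix changes neither n nor the threshold.

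**3. Primary endpoint, illustration only.** The documents give no rate of added therapy. Let k be an assumed expected number of the 120 who count as responders only because of an unlisted treatment, with a device-attributable rate of exactly 50%. The chance of success is P(X ≥ 72) at p = 0.50 + k/120:

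| k (assumed) | Chance of reaching 72/120 |
|---|---|
| 0 | 1.8% |
| 1 | 2.7% |
| 2 | 4.1% |
| 3 | 6.0% |

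The nominal level is 2.5%.

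**4. First labeling secondary, illustration only.** The Phase I baseline is 4.1 episodes per day, and the change at the final trial visit is 3.3 ± 1.7 (Protocol 3.1.2.1). Assume a share s of subjects is on a drug with a 50% fall. Setting them to no change lowers the mean improvement by s × 0.5 × 4.1:
- s = 2%: 0.04 per day
- s = 5%: 0.10 per day
- s = 10%: 0.21 per day

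Read as inflation, this is near an upper bound, because it gives the whole fall to the drug and none to the implant.

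For the test against zero, holding the SD at 1.7, SE = 1.7/√120 = 0.155. The statistic moves from 3.3/0.155 ≈ 21 to (3.3 − 0.21)/0.155 ≈ 20. With half the Phase I effect it is (1.65 − 0.21)/0.155 ≈ 9. In that last case the SD would have to exceed 1.44 × √120 / 1.96 ≈ 8 for the test to fail.

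**The case against.** The case against is substantial.

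- **Such use should be rare.** Exclusion 14 removes people unwilling to avoid TNS. Those who leave for lack of efficacy, or are explanted before the endpoint for any reason, are already failures (SAP 5.6.2 and 5.7), which catches many who would switch treatment. This stands, and it makes the gap narrow. It does not close it: an entry criterion on willingness does not say how an observed outcome is counted, and the sponsor wrote a failure rule for OAB drugs although those are also barred.
- **The Per Protocol analysis might drop these subjects.** It might, if the use is judged a deviation that significantly affects the primary endpoints. That analysis is supportive only.
- **BoNT-A can be read as a medication.** That is reasonable, but the term is undefined and the reading should be settled before the analysis.
- **Failing everyone with a logged therapy would misclassify device responders.** A reader might infer that any entry in the therapy log should mean failure. That goes too far: a genuine responder who resumes pelvic floor exercise would become a device failure. Inclusion 10 already requires that conservative treatment had failed or was unsuitable.
- **The primary and secondary rules contradict each other.** A reader might infer this too, but the documents do not support it. Counting drug users as failures in a binary endpoint and using observed values in a continuous one is a recognised pair of estimands. SAP 5.6.4 uses the no-change value only where evaluable data are lacking, so observed diaries should not be overwritten in the main analysis. What is missing is a sensitivity analysis.

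**Conclusion.** The point holds in a limited form. As written, the plan would count a completer helped by TNS, and arguably by BoNT-A, as a device responder. It would also enter drug users in the labeling secondaries at on-drug values with no check on the effect.

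The size is unknown and probably small. A one-subject change decides the trial only if the count lies at 71 or 72 of 120. The rise to 4.1% or 6.0% rests on an assumed two or three such subjects and a true device rate of exactly 50%.

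A reader might infer that the responder rate is in fact biased, or that a labeling test could be overturned. The documents support neither. They report no added-therapy use, and a shift of 0.04 to 0.21 episodes per day could not plausibly alter a test of mean UUI change against zero. It could slightly alter an estimate quoted in labeling. The other hierarchical secondaries were not quantified. The change is worth making because it is cheap and removes a judgement that would otherwise be made with the data in view.

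**What to change.** - **SAP 5.6.2 and Protocol 6.1.2.3:** extend the failure rule to a pre-specified list of active OAB treatments (OAB medications, TNS and BoNT-A) used after the same two-week point and before the Month 6 endpoint. Identify cases from the medication and therapy records. State that conservative and behavioural measures are not on the list.
- **SAP 5.6.4:** add a sensitivity analysis of the hierarchical secondaries that sets these subjects to no change on the continuous endpoints and to non-responder on the ICIQ-OABqol 10-point endpoint. Keep observed values as the main analysis.

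The cost is a few sentences in two documents, some extra analysis, and possibly slightly less favourable estimates. No new data are needed. The change concerns only how outcomes are counted, not what care is given.
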